8.3. Adverse Events

All AEs will be recorded from the time of the treatment through the end of the observational period. Adverse events onset or worsening, on or after the study drug administration are considered TEAEs. TEAEs will be tabulated by treatment group for all subjects in the SfAS and will be flagged in the "all AEs" listing. Adverse events will be coded using Medical Dictionary for Regulatory Activities (MedDRA). Any ear-related AE, whether occurring in 1 or both ears, will only be counted at most once in subject-level counts per system organ class (SOC) and preferred term (PT).

The following analyses will be conducted:

- Overall summary of TEAEs
- Overall summary of TEAEs by SOC and PT
- Overall summary of TEAEs presented by maximum severity (Mild, Moderate, or Severe), by SOC and PT
- Overall summary of TEAEs presented by maximum relationship (Related, Possible, Unlikely or Not Related) to study drug, by SOC and PT

For ear-related TEAE analyses where the ear is the unit of analysis, an event will be attributed its occurrence to either the treated ear, the untreated ear, or both ears. The ear-related TEAE analyses will be conducted by treatment group for the following:

- Overall summary of ear-related TEAEs presented by ear attribution, by SOC and PT
- Overall summary of ear-related TEAEs presented by ear attribution, by phase (up to Day 30, Day 30-90, and after Day 90), SOC and PT
- 8.3.1. Imputation Rules for Missing AE Date/Time of Onset/Resolution

Partial dates will be imputed for the purposes of defining TEAEs as follows:

- For a missing start day where the month and year are present, the start day will be set to the first day of the month, unless the following two conditions are met:
 - 1. the first day of the month is before the date of administration of study drug and the month and year are the same as the month and year of the date of administration of study drug, and
 - 2. the end date is on or after the date of administration of study drug or the end date is completely missing.

If the two above conditions are met, the start day will be set to the day of administration of study drug.

• For a missing start day and month where the year is present, the start day and month will be set to January 1st, unless 1) January 1st is before the date of

administration of study drug and the year is the same as the year of the date of administration of study drug, and 2) the end date is on or after the date of administration of study drug or the end date is completely missing, in which case the start day and month will be set to that of the date of administration of study drug.

- For a missing end day where the month and year are present, the end day will be set to the last day of the month, unless the month and year are the same as the month and year of the last contact date for the subject, in which case the end day will be set to that of the subject's last contact date, which is captured in SDTM as DM.RFPENDTC (Date/Time of End of Participation) with derivation rule specified in the study SDTM specifications.
- For a missing end day and month where the year is present, the end day and month will be set to the subject's last contact date, unless the year of the subject's last contact date is greater than the end year, in which case the end day and month will be set to December 31st.

Completely missing dates will be imputed for the purposes of classifying TEAEs as follows:

- For an entirely missing start date (i.e., day, month, and year are missing), the start date will be set to the date of administration of study drug unless the end date is prior to the date of administration of study drug, in which case the start date will be set to the end date.
- 8.4. Deaths, Serious Adverse Events, and Other Significant Adverse Events

Treatment-emergent SAEs, TEAEs leading to study withdrawal, and fatal TEAEs will be summarized for all subjects in the SfAS by treatment group for the following:

- Overall summary of SAE by SOC and PT
- Overall summary of TEAE leading to study withdrawal by SOC and PT
- Overall summary of fatal TEAE by SOC and PT

SAEs, adverse events leading to study withdrawal, and fatal AEs will be presented in data listings for subjects in the SfAS.

Adverse Events of Special Interest (AESI), defined in the Protocol, will be summarized by treatment group, SOC, and PT for all subjects in the SfAS. AESIs that occur after study treatment injection will be presented in a data listing for subjects in the SfAS.

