## **14 ADVERSE EVENTS**

### **Adverse Event Definition**

An AE is defined as any untoward medical occurrence in a clinical study subject administered a medicinal product which does not necessarily have a causal relationship with this treatment. An AE can therefore be any unfavorable and unintended sign (including an abnormal laboratory finding), symptom, or disease temporally associated with the use of a medicinal (investigational) product, whether or not it is related to the medicinal (investigational) product. This includes an exacerbation of pre-existing conditions or events, intercurrent illnesses, drug interaction or the significant worsening of the indication under investigation that is not recorded elsewhere on the CRF under specific assessments. Anticipated fluctuations of pre-existing conditions, including the disease under study that do not represent a clinically significant exacerbation or worsening need not be considered AEs.

It is the responsibility of the investigator to document all AEs that occur during the study. AEs will be elicited by asking the subject a nonleading question, for example, "Have you experienced any new or changed symptoms since we last asked/since your last visit?". AEs will be recorded from the time of study treatment (Visit 3) through the end of the observational period, or final study visit. AEs should be reported on the appropriate page of the CRF.

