## **Adverse Events of Special Interest (Audiometric and Otoscope)**

If any of the following criteria are met through Visit 6 (Day 90), the event will be recorded as an adverse event of special interest (AESI) per ASHA guidelines (ASHA 1994):

- Asymmetric loss of hearing greater than or equal to 20 dB at any one frequency in the treated ear compared to Visit 3.
- Asymmetric loss of hearing greater than or equal to 10 dB at two adjacent frequencies in the treated ear compared to Visit 3.
- Asymmetric loss of response at three consecutive test frequencies where responses were previously obtained in the treated ear compared to Visit 3.

For word recognition testing, a follow up visit score through Visit 6 (Day 90) in the treated ear that falls below the lower limit of the 95% confidence interval of the Visit 3 word recognition score will be considered an AESI (Carney and Schlauch, 2007).

Additionally, if the subject experiences a perforation greater than 25% of the tympanic membrane in the treated ear through Visit 6 (Day 90) this will be recorded as an AESI.

If any subjects in the study experience the same AESI through Visit 6 (Day 90), the Medical Monitor will discuss these with the Principal Investigators and each subject's condition will be discussed.

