Each subject will be placed in the supine position. Topical anesthesia (with the exception of phenol) will be administered directly to the tympanic membrane in the study ear. Under a microscope, a 25-gauge needle will be used to inject FX-322 or placebo into the middle ear at the junction of the posterior inferior and posterior superior quadrant with the needle tip directed towards the round window. The posterior superior quadrant should be avoided to prevent injury to the ossicles. After injection, the subject will continue to lie with the injected ear facing up for 20-30 minutes. The injections will be performed at an appropriate location designated by a Board-certified Otolaryngologist trained and experienced in performing intratympanic injections. Safety monitoring will include recording of adverse events (AEs), monitoring of audiology, tympanometry, otoscopic exams, and Columbia-Suicide Severity Rating Scale (C-SSRS) assessments.

Follow-up: Subjects will be required to return to clinic for safety, otologic, and audiologic assessments at Days 30 (Visit 4), 60 (Visit 5), and 90 (Visit 6) following the study injection. Unscheduled visits may occur as needed.

Observation: Subjects will return to clinic for safety, otologic, and audiologic assessments at Days 180 (Visit 7) and 270 (Visit 8).

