5. STUDY SUBJECTS

5.1. Disposition of Subjects

The disposition of all consented subjects will be tabulated by treatment group and overall. Subjects who failed screening or were not randomized will only be included in the overall column. The following disposition information will be summarized:

Version Date: 2023-01-19

Page 14 of 64

- The number of subjects consented (signed Informed Consent)
- The number and percentage of subjects who failed screening and the reasons for failure
- The number of subjects not randomized and the number of subjects randomized
- The number of subjects in the FAS
- The number and percentage of subjects in the PPAS and SfAS analysis sets
- The number and percentage of subjects who completed the study through Day 90 (Visit 6)
- The number and percentage of subjects who discontinued the study early and the reasons for withdrawal
- The number and percentage of subjects who discontinued the study early for reasons related to COVID-19
- The number and percentage of subjects who continued to the Observational period
- The number and percentage of subjects who completed Day 180 (Visit 7) and Day 270 (Visit 8)
- The number and percentage of subjects who did not complete Day 180 (Visit 7) and Day 270 (Visit 8) and the reasons not completed
- The number and percentage of subjects who did not complete Day 180 (Visit 7) and Day 270 (Visit 8) for reasons related to COVID-19

Percentages for the number of subjects who failed screening and the reasons for failure will be based on the number of consented subjects. All other percentages will be based on number of subjects in the SfAS.

Duration of study follow up (from randomization date to study completion date or early discontinuation visit date) will be summarized in a Kaplan-Meier curve for all randomized subjects by treatment group. Subjects who completed the study will be censored at the study completion date.

Subject disposition data for all randomized subjects will also be listed. A separate bysubject listing for screen failures will be generated along with reason for screen failure.

A listing of all subjects affected by the COVID-19 pandemic (discontinued the study early, had remote visits performed, or missed visits for reasons related due to COVID-19) will be provided to list the impacts of the pandemic on the subject's participation.

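### The SAP 8.3 split of ear-related adverse events by phase needs denominators of subjects still observed and one rate per unit time

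*SAP*

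**What the plan says.** SAP 8.3 lists a descriptive summary of ear-related TEAEs by treatment group and by ear attribution (treated, untreated or both), "by phase (up to Day 30, Day 30-90, and after Day 90), SOC and PT". For TEAEs in general the same section says "TEAEs will be tabulated by treatment group for all subjects in the SfAS". It gives no separate denominator for a phase. For the ear-related summaries it names the ear, not the subject, as the counting unit, but does not say which statistic goes in the cells. Protocol 15.6.1 plans numbers and percentages of subjects for adverse events.

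SAP 2.2.2 sets follow-up "assessments at Days 30 (Visit 4), 60 (Visit 5), and 90 (Visit 6) following the study injection", then observation visits at Days 180 and 270. Collection runs over the whole period: "All AEs will be recorded from the time of the treatment through the end of the observational period". Protocol 14 describes how events are found: "AEs will be elicited by asking the subject a nonleading question" about symptoms since the previous contact.

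On who is still under observation, SAP 5.1 lists as a disposition item "The number and percentage of subjects who continued to the Observational period", with further counts of those who did and did not complete Days 180 and 270. Protocol 10.4 defines study completion by the follow-up visits up to Day 90.

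The audiometric, word-recognition and perforation triggers for events of special interest stop at Day 90 (Protocol 14): "If any of the following criteria are met through Visit 6 (Day 90), the event will be recorded as an adverse event of special interest".

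SAP 8.2 summarizes exposure as counts of doses given. Neither document plans person-time or exposure-adjusted adverse event rates.

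**The concern.** A table split by time since injection invites one question: do ear events cluster around the procedure, fade, or persist? Percentages over windows of about 30, 60 and 180 days do not answer it, because a longer window collects more events at the same underlying risk. Two features of the last phase work the other way. Subjects who have left still count in a denominator made of the whole safety set, and questioning falls from once per 30 days to once per 90 days, which may lower reporting. The net direction in real data is therefore unknown.

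Safety is the trial's secondary objective, and this is the only adverse event summary listed in the SAP that is split by time since injection. If more subjects in one arm than in the other leave after Day 90, the late-phase contrast between arms would also shift without any difference in risk.

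**Working it through.** **Inputs from the documents.** Visit days 30, 60, 90, 180 and 270 (SAP 2.2.2); phase boundaries at Days 30 and 90 (SAP 8.3); 124 randomized, 112 evaluable, 10% dropout (SAP 2.5).

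**Inputs assumed, because the documents give none.** A constant hazard with a 30-day risk r of an ear-related event of 2%, 5% or 10%, and a share c of the safety set continuing after Day 90 of 100%, 90%, 75% or 50%. For simplicity, everyone is observed to Day 90, those who continue are observed for all 180 days, and each cell counts subjects with at least one event in the phase.

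**The plan's own figure.** The documents state no figure for this table. The nearest is the dropout adjustment: 112 / (1 − 0.10) = 124.4, against the stated target of 124, so it reproduces to rounding. It says nothing about continuation after Day 90.

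**Step 1: phase lengths and visits.** 30 − 0 = 30 days; 90 − 30 = 60 days; 270 − 90 = 180 days. Scheduled visits number 1, 2 and 2, or 1/1 = 1, 2/2 = 1 and 2/6 = 0.33 per 30 days.

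**Step 2: percentage with an event at constant risk.** With λ = −ln(1 − r)/30, the expected share over d days is 1 − exp(−λd) = 1 − (1 − r)^(d/30). For r = 5%: 1 − 0.95 = 5.0%; 1 − 0.95² = 9.8%; 1 − 0.95⁶ = 26.5%.

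**Step 3: whole safety set as denominator.** The last-phase figure becomes c × [1 − (1 − r)⁶].

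| 30-day risk | Up to Day 30 | Day 30-90 | After Day 90, c = 100% | c = 90% | c = 75% | c = 50% |
|---|---|---|---|---|---|---|
| 2% | 2.0% | 4.0% | 11.4% | 10.3% | 8.6% | 5.7% |
| 5% | 5.0% | 9.8% | 26.5% | 23.8% | 19.9% | 13.2% |
| 10% | 10.0% | 19.0% | 46.9% | 42.2% | 35.1% | 23.4% |

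With no change in risk, the last phase is 4.7 to 5.7 times the first under full follow-up, and 2.3 to 2.9 times if half continue.

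**Step 4: the reverse case.** Suppose the first and last phases show equal percentages under full follow-up. Then λ₃ × 180 = λ₁ × 30, so λ₃/λ₁ = 30/180 = 1/6. A sixfold fall in risk would look flat.

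**Step 5: arms with equal risk and unequal continuation.** With an assumed 90% continuing in one arm and 75% in the other, the last-phase figures are 10.3% and 8.6% (r = 2%), 23.8% and 19.9% (r = 5%), or 42.2% and 35.1% (r = 10%). With subjects entering the phase as denominator, both arms show the same figure (11.4%, 26.5% or 46.9%).

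**Step 6: what each part of the remedy does.** A denominator of subjects entering the phase removes dilution from those who leave before it, but not the length effect: at r = 5% the last phase is 26.5/5.0 = 5.3 times the first. A rate removes the length effect: −100 × ln(1 − r) gives 2.02, 5.13 or 10.54 events per 100 subject-months of 30 days, the same in all three phases.

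**The case against.** Several objections stand and limit the point.

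- **No cross-phase comparison is planned.** The table is descriptive and by arm. Within a phase both arms, and both ears of a subject, share the same window, visit schedule and recall interval. A reader might infer that unequal phase lengths bias FX-322 against placebo. They do not; only unequal continuation could.
- **The cell statistic and phase denominator are inferred.** They are read from the general safety-set sentence and Protocol 15.6.1. SAP 1 places table specifications in separate documents, which may settle the matter. Still, the safety set is the only denominator the SAP states.
- **Incomplete continuation is foreseen, not shown.** SAP 5.1 plans a count and reports none. Protocol 11.1 asks for every effort to complete the observation visits, and SAP 7.1.6 expects little missing data. The lower continuation shares used above have no source in the documents.
- **A constant hazard is not the expected pattern.** The protocol describes earlier adverse events as tied to the injection procedure and transient. A reader might take the roughly fivefold figure as a forecast of a false late rise, but the documents do not support that. Step 4 shows that front-loaded events can also be misread, in the opposite direction.
- **This is not the only view of ear safety over time.** Otoscopy and tympanometry are summarized by visit for treated ears with shift tables (SAP 8.6.3, 8.6.4), and retention by arm appears in the disposition table.
- **The limit on events of special interest is secondary.** It is explicit, those events have their own summary, and ordinary adverse events are still recorded after Day 90.

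The disposition counts let a reader see late retention by arm, but they do not correct the percentages in the event table.

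**Conclusion.** The point holds as a low-impact improvement. With the whole safety set as the only stated denominator, late-phase percentages are diluted by subjects no longer observed and percentages are not comparable across phases. The late arm comparison could be distorted if continuation differs by arm. What changes with phase length by construction is the cumulative percentage, not the rate of events.

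The size cannot be stated, because neither an ear-event rate nor a continuation share is given. Under the assumed constant 5% risk per 30 days, the last-phase figure would range from 13.2% (half continuing) to 26.5% (all continuing), against 5.0% in the first phase. Unequal continuation of 90% and 75% would open a gap of about 4 points between arms of equal risk. These figures illustrate the mechanism and do not predict the result. The primary and key secondary efficacy analyses are unaffected.

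**What to change.** In SAP 8.3, for the summary of ear-related TEAEs by phase:

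1. For each phase and arm, show the number of subjects still under observation at its start and use that number as the denominator.
2. For any ear-related TEAE by ear attribution, add events per 100 subject-months in each phase, with time ending at the last visit or contact. Do not do this for every SOC and PT, where counts will be too small.
3. Assign Day 30 to one phase; as worded it falls in the first two.
4. Footnote the phase lengths, and that the criteria for events of special interest apply only through Day 90.

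The cost is a short wording change and one programming change. SAP 8.3.1 already uses a last contact date captured in the data, so no new data are needed. The drawbacks are that denominators will differ between phases and, with about 62 subjects per arm, the rates may rest on few events.

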8.5. Urine Pregnancy Tests

Urine pregnancy test results will be included in a listing for subjects in the SfAS.

8.6. Vital Signs, Physical Findings, and Other Observations Related to Safety

8.6.1. Vital Signs

Vital signs collected on the CRF will be provided in a listing for subjects in the SfAS. The number and percentage of subjects with clinically notable vital signs as defined below will be summarized for post-baseline visits by treatment group for subjects in the SfAS.

- Systolic blood pressure (BP)
 - \geq 180 mmHg and an increase \geq 20 mmHg from baseline
 - \circ ≤90 mmHg and a decrease ≥20 mmHg from baseline
- o Diastolic BP
 - \geq 105 mmHg and an increase \geq 15 mmHg from baseline
 - \circ ≤50 mmHg and a decrease ≥15 mmHg from baseline
- o Heart rate
 - \geq 120 bpm with an increase from baseline of \geq 15 bpm
 - \circ ≤50 bpm with a decrease from baseline of ≥15 bpm
- o Temperature
 - >38 °C
 - o <35 ℃

Unscheduled visit and early termination visit data will not be mapped to scheduled visits per Section 7.1.2. Unscheduled visit and early termination visit data will be excluded from summary tables and included in listings.

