## **11 DISCONTINUATION AND LOST TO FOLLOW-UP**

### **11.1 Discontinuation**

If a clinically significant finding is identified (including, but not limited to changes from baseline) after randomization, the investigator or qualified designee will determine if any change in participant management is needed. Any new clinically relevant finding will be reported as an adverse event (AE).

The data to be collected at the time of study discontinuation will include the following:

- All efforts will be made for the subject to complete all of the follow up and observational visits.
- If the subject does not wish to continue the follow up period, all efforts will be made for the subject to complete all designated assessments collected at the Visit 6 (Day 90)/Follow-up ET Visit.

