#### **12.4 Follow-up (Visit 4, [Day 30 +/- 5 days])**

The Follow-up Visit (Visit 4) will take place at Day 30 ( $\pm$  5 days). The following procedures will be performed at the Follow-up Visit:

- Record any AEs that have occurred since the last visit and any changes in concomitant medication
- Perform Columbia Suicide and Severity Scale
- Perform otoscopy, standard pure tone audiometry, speech reception threshold, extended high frequency audiometry, word recognition testing (Maryland CNC and W-22), WIN testing (NU-6), and tympanometry
- Record vital signs

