7.1.2. Assessment Time Windows

For by-visit summaries, the nominal visit will be used for analysis. Unscheduled visits will be listed but will not be displayed separately in the summaries.

Analysis windows listed in Table 7-1 will be used in the efficacy analyses for slotting actual efficacy assessment date into planned assessment schedule. Early termination visit and unscheduled visit efficacy data will be included in the analyses if no scheduled visit data is available for the nominal CRF visit. If more than one unscheduled assessment (early termination or unscheduled) is performed within an analysis window, the assessment performed closest to the target day will be used.

Visit	Visit Number	Assessment /Day	Target Day	Target Window	Analysis Window ^a
Screening/ Start of Lead-In	1	-40 to -30	N/A	N/A	N/A - Nominal CRF visit
Lead-In Visit	2	-26 to -12	Visit 1 + 16 days	Target day (+/- 2 days)	N/A - Nominal CRF visit
End of Lead-In/ Treatment	3	1	Visit 1 + 35 days	1/Target day (+/- 5 days)	1
In-Clinic Follow-up	4	30	30	25-35 (+/- 5 days)	2-45
In-Clinic Follow-up	5	60	60	55-65 (+/- 5 days)	46-75

In-Clinic Follow-up	6	90	90	85-95	76-135
/Early Termination				(+/- 5 days)	
(ET)					
In-Clinic	7	180	180	173-187	136-225
Observation				(+/- 7 days)	
In-Clinic	8	270	270	263-277	≥226
Observation				(+/- 7 days)	
^a Analysis windows for the Screening and Lead-In Visit are not defined and visit assignments					
are based on the nominal CRF visits. Analysis windows for visits on or after randomization					
are defined using the mid-points between each scheduled visit and will be used to map early					

[figure not shown]

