8.6.4. Tympanometry

Pa	ge 46 of 64
Version Date: 2023-01-19	Version: 2.0

Tympanometry will be performed at the Screening/Start of Lead-In, End of Lead-In/Treatment, Day 30, Day 60, Day 90, Day 180, and Day 270 visits. Tympanometry data including type of tympanogram, ear canal volume, peak admittance, and peak pressure will be summarized descriptively for treated ears by visit and treatment group for subjects in the SfAS. A tympanogram classification shift table for treated ears from baseline to postbaseline visits will also be produced by treatment group. Unscheduled visit and early termination visit data will not be mapped to scheduled visits per Section 7.1.2. Unscheduled visit and early termination visit data will be excluded from summary tables and included in listings.

All tympanogram data for both treated and untreated ears, scheduled and unscheduled, will be presented in a data listing for subjects in the SfAS.

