13. APPENDICES

13.1. Study Flow Chart

13.2. Schedule of Assessments

Visit	Screening/ Start of Lead-In	Lead-In Visit	End of Lead-In/ Treatment	In-Clinic Follow-up	In-Clinic Follow up	In-Clinic Follow-up / ET ^e	In-Clinic Observation	In-Clinic Observation	Un-scheduled Visit
Visit Number	1	2	3	4	5	6	7	8	UNS
Assessment/Day	Day -40 to -30	Visit 1 + 16 days	Visit 1 + 35 days	Day 30	Day 60	Day 90	Day 180	Day 270	
Visit Window	N/A	+/- 2 days	+/- 5 days	+/- 5 days	+/- 5 days	+/- 5 days	+/- 7 days	+/- 7 days	N/A
Informed Consent	X								
Inclusion/ Exclusion Criteria	X ^a	Xa	Хр						
Eligibility Assessment by EDC	X	X	Хр						
Demographics	Xª								
Medical History	Xª	X ^a	Хр						
Concomitant Medication	Xª	Xª	X ^{b, c}	Х	Х	X	Х	Х	Х
Physical Examination including weight and height	X								X ^d
Vital Signs (body temperature, pulse rate, bp)	Х	X	Хр	Х	Х	X			X ^d
Tympanometry	Х		Хр	Х	Х	X	Х	Х	X ^d
Standard Pure Tone Audiometry	Х	X	Xb	Х	Х	X	Х	Х	X ^d
Speech Reception Threshold (SRT)	Х	Х	Х	Х	Х	X	Х	Х	X ^d
Extended High Frequency Audiometry	X	Х	Хр	Х	Х	Х	Х	Х	X ^d
Word recognition, quiet (Maryland CNC)	X	X	Xb	Х	Х	X	Х	Х	X ^d
Word recognition (W-22)	Х	Х	Хр	Х	Х	X	Х	Х	X ^d
Words in noise (WIN)	Х	Х	Хр	Х	Х	X	Х	Х	X ^d
Tinnitus Functional Index	Ī		Xb			X	Х	Х	X ^d

Page 53 of 64

Version Date: 2023-01-19

Statistical Analysis Plan 19 January 2023

Visit	Screening/ Start of Lead-In	Lead-In Visit	End of Lead-In/ Treatment	In-Clinic Follow-up	In-Clinic Follow up	In-Clinic Follow-up / ET ^e	In-Clinic Observation	In-Clinic Observation	Un-scheduled Visit
Visit Number	1	2	3	4	5	6	7	8	UNS
Assessment/Day	Day -40 to -30	Visit 1 + 16 days	Visit 1 + 35 days	Day 30	Day 60	Day 90	Day 180	Day 270	
Visit Window	N/A	+/- 2 days	+/- 5 days	+/- 5 days	+/- 5 days	+/- 5 days	+/- 7 days	+/- 7 days	N/A
Qualitative									
Columbia Suicide Severity Rating Scale			Хр	Х	Х	X	Х	Х	X ^d
PGI-S Hearing Loss Scale			Хр						
PGI-S Daily Impacts Scale			Xb						
PGI-C Hearing Loss Scale						X			
PGI-C Daily Impacts Scale						X			
Otoscopy	X		Хр	X	Х	X	X	X	X ^d
Urine Pregnancy Test (women of childbearing potential only)	Х		Хр			Х			X ^d
Randomization by EDC			Хр						
Study Medication (FX-322 or placebo)			Х						
Adverse Events			X¢	Х	Х	Х	Х	Х	Х

a- Performed during the Screening Visit and again if a subject notes a change in their medical status during the lead in period

b – Assessment performed prior to injection

c- Assessments performed after injection

d- Perform at Investigator Discretion

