e- If a subject discontinues prior to Visit 6 (Day 90), all efforts should be made to complete the Visit 6 (Day 90) In-Clinic Follow-up/Early Termination (ET) Visit as soon as possible and, whenever possible, prior to starting any new medication or treatment.

Page 54 of 64

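### Otoscopy, tympanometry and notable-vital-sign tables leave out unscheduled and early-termination exams, so findings seen only there are tabulated only if they are recorded as an AE or AESI

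*SAP*

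**What the plan says.** SAP 8.6.1 (vital signs), 8.6.3 (otoscopy) and 8.6.4 (tympanometry) carry the same two-part rule. First, "Unscheduled visit and early termination visit data will not be mapped to scheduled visits per Section 7.1.2". Second, "Unscheduled visit and early termination visit data will be excluded from summary tables and included in listings". The rule covers the count of clinically notable vital signs, the by-visit otoscopy and tympanometry summaries, and the two shift tables.

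The exams it removes are foreseen in the plan. SAP 2.2 says of the follow-up period: "Unscheduled visits may occur as needed". The schedule in SAP 13.2 allows otoscopy, tympanometry and vital signs at such visits at the investigator's discretion. For subjects who leave before Day 90, a footnote to that schedule says "all efforts should be made to complete the Visit 6 (Day 90) In-Clinic Follow-up/Early Termination (ET) Visit as soon as possible". Protocol 10.5.4 likewise asks for the completers' final evaluations, with stress on safety.

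For efficacy, SAP 7.1.2 takes the other course: "Early termination visit and unscheduled visit efficacy data will be included in the analyses if no scheduled visit data is available".

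Changes in otoscopy and tympanometry are named safety endpoints in Protocol 9. Vital signs are not on that list, but they are part of the planned safety analyses (Protocol 15.6, SAP 8.1).

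**The concern.** An unscheduled exam is often done because something seems wrong, and an early-termination exam is the last look at a subject who is leaving. A rule that keeps both out of the endpoint-specific tables can remove the exams most likely to show an abnormality. Protocol 8.2 lists persistent perforation, bleeding and middle ear infection among the risks of an intratympanic injection, and no scheduled exam falls in the first weeks after it.

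The AE tables are the other route, but for smaller findings they depend on the investigator deciding that a finding is clinically relevant. The shift tables and the fixed numeric vital-sign criteria do not depend on that judgement. If they omit these exams, a reader comparing arms could see fewer abnormal findings than were recorded, and the remainder would have to be found by reading listings.

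**Working it through.** The plan gives no figure for this point, so the check compares provisions, with two small calculations.

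**1. The interval without a scheduled exam.**
- Day 1: otoscopy, tympanometry and vital signs at Visit 3 carry the footnote "Assessment performed prior to injection" (SAP 13.2).
- Next scheduled exam: Protocol 12.4 says "The Follow-up Visit (Visit 4) will take place at Day 30", with a window of 5 days either side. 30 − 5 = Day 25 and 30 + 5 = Day 35, which reproduces the target window in SAP Table 7-1.
- Gap after the Day 1 injection: 25 − 1 = 24 days to 35 − 1 = 34 days.

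Any otoscopy, tympanometry or vital-sign assessment after injection and before Visit 4 is therefore unscheduled or early termination, and SAP 8.6 keeps it out of these tables.

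**2. Other routes into a safety table.**

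| Route | Source | What it captures |
|---|---|---|
| AE | Protocol 11.1 and 14; SAP 8.3 | New findings judged clinically relevant, at any visit; ear-related events are tabulated by period, the first ending at Day 30 |
| AESI | Protocol 14; SAP 8.4 | Perforation above 25% of the membrane, and set audiometric and word-recognition losses, through Day 90 |
| AE leading to withdrawal | SAP 8.4 | Events recorded as the cause of leaving |
| Still present at a scheduled visit | SAP 8.6 | By-visit and shift tables; notable-vital-sign count |

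What remains outside every table must meet three conditions together: seen only at an unscheduled or early-termination exam, not recorded as an AE or AESI, and absent at every scheduled post-baseline visit.

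**3. A ceiling for the early-termination part.** SAP 2.5 gives 112 evaluable subjects, 10% dropout and 124 enrolled. 112 / 0.9 = 124.4, so 124 agrees to rounding. Dropouts: 0.10 × 124 = 12.4, or 124 − 112 = 12; per arm, 0.10 × 62 = 6.2.

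This counts exams that could be left out, not abnormal findings. Neither document gives a rate of unscheduled exams or of findings at them, so the number of findings missed cannot be computed.

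**4. Would the efficacy rule close the gap?** Only in part. SAP 7.1.2 uses unscheduled or early-termination data when the scheduled visit is missing. A subject with an abnormal exam on, say, Day 10 and a normal one at Visit 4 would still show only the normal result. An any-visit summary is needed to capture the first.

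**The case against.** A reader might infer that abnormal findings before Day 25, or at withdrawal, never reach a safety table. The documents do not support that. Protocol 11.1 sends every new clinically relevant finding to AE reporting with no limit to scheduled visits, and the AE definition in Protocol 14 includes unfavourable signs. The 25% perforation threshold defines an AESI, not an AE, so a smaller perforation can still be recorded as an AE. SAP 8.3 tabulates ear-related events in a period ending at Day 30, which covers the interval in question. All of this stands, and it reduces the gap to the three-condition remainder.

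It is also fair to say that:
- A transient sign in a subject who has no unscheduled visit is never observed. No table row can recover it; that follows from the schedule, not from the analysis rule.
- Twelve is a ceiling. SAP 7.1.6 expects very little missing data, subjects lost to follow-up may have no final exam, and those who leave after Day 30 or Day 60 still contribute earlier scheduled exams.
- Vital signs fit less well. They are not a named safety endpoint, and the concern about procedure-related harm is about the membrane and middle ear.
- The exclusion is stated openly and the data are listed. By-visit and shift tables are what the protocol synopsis promises.
- An any-visit count rises with the number of visits, so it is not a clean rate.

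These points lower the weight of the concern, especially for vital signs. They do not remove it for otoscopy and tympanometry: the remaining route for a smaller or silent finding depends on judgement, and the plan gives no reason for leaving its recorded exams out of every summary of those endpoints.

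**Conclusion.** The concern holds in a limited form. Under the stated rule, a finding seen only at an unscheduled or early-termination exam is tabulated only if it becomes an AE or AESI or persists to a scheduled visit; if not, it is in listings only. The findings exposed are those that need judgement to become an AE: a perforation of 25% or less, a tympanogram-type change, or a vital sign past the SAP's thresholds but not judged clinically relevant.

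The size in findings is unknown. The only bound available is at most about 12 of 124 subjects (about 6 per arm) with an early-termination exam left out of the tables, assuming the planned 10% dropout and that every such subject has that exam. Unscheduled exams come on top and cannot be counted from the documents.

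The point does not touch the sample size, type I error or the efficacy analyses. It is a gap in safety presentation that is cheap to close and should be closed.

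**What to change.** In SAP 8.6.3 and 8.6.4, keep the scheduled by-visit summaries and shift tables as they are. Add to each shift table one row by arm, on the Safety Analysis Set and for treated ears: *worst post-baseline result at any visit, including unscheduled and early-termination visits*. State how worst is defined. For otoscopy, any abnormal finding would do. For tympanometry the SAP gives no ranking of tympanogram types, so it should either set one or count any change from the baseline classification.

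As a lesser addition in SAP 8.6.1, count subjects with a clinically notable vital sign over all post-baseline assessments, next to the existing counts. Then amend the exclusion sentence in all three sections so that it applies to the by-visit rows only.

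The cost is a SAP wording change and one extra row per table. The data are already collected and listed, and no visit or exam is added. The drawback is that the any-visit row depends on how often subjects are seen, and could differ between arms for that reason alone. Show it beside the scheduled-visit rows and say so in a footnote.
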